## **9.2 Transfused Blood Products**

The types and numbers of units of blood products transfused will be recorded from the onset of screening through Day 6. Within multiple tabular and graphic summaries of transfusions, the number of units transfused at any given assessment will be defined as the total number of units transfused after the previous assessment and before/during the given assessment. Baseline reporting will be limited to the blood products transfused during the 24 hours immediately preceding Thrombosomes infusion; it should then follow that all units reported before such time will be reported as occurring during screening. Lastly, the number of whole blood platelet derived units will be expressed as 1 unit, equivalent to a single platelet apheresis unit per the transfusing facility's standard.

In a single table, the numbers and percentages of patients who receive transfusions will be summarized by visit, reason for transfusion (active bleeding surgical, active bleeding non-surgical, low platelet count, chronic disease, marrow hypoplasia, coagulopathy, and other), and blood product type (packed red blood cells, whole blood, apheresis platelets, pooled whole blood derived platelets, cryoprecipitate, and plasma). In a second table, the number of blood product units transfused (treated as a continuous variable) will be summarized by blood product type and visit using descriptive statistics. For visual assessment of the number of platelet units transfused through time, a panel of spaghetti plots will be provided, with each plot representing a single patient cohort and displaying an overlay of the raw numbers of platelet units transfused through time for individual patients. Lastly, 2 clustered bar charts will be constructed to display the mean number of platelet transfusions received per patient within the first 24 hours following infusion and during Days 3-6, with the bars representing patient cohorts and the clusters of bars (cohorts) being defined by nominal visit within the time-frame of interest. Details describing all transfusions, as well as all products comprising the transfusions, will be presented in a patient-level data listing.

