All enrolled patients with active bleeding of modified WHO Grade 1 (subset of patients with either epistaxis, hematuria, oral petechiae, oropharyngeal bleeding, or bleeding at invasive or other wound sites) or Grade 2 bleeding will receive Thrombosomes. Grades 0, 3, or 4 bleeding are not inclusion criteria for enrollment. Active bleeding is defined as to occur within 4 days of infusion. If the patient progresses to grade 3 or 4 bleeding during that time, they will be excluded from the study and will not be infused. Doses will be adjusted per weight of each patient. The starting dose for patients in Cohort 1 will be approximately 5 ml of Thrombosomes or approximately  $9.45 \times 10^7$  particles/kg or 165 TGPU per kg by IV infusion. The dose for patients in Cohort 2 will be approximately 10 ml of Thrombosomes or approximately  $1.89 \times 10^8$  particles/kg or 330 TGPU per kg by IV infusion. The dose for patients in Cohort 3 will be one dose of approximately 20 ml of Thrombosomes or approximately  $3.78 \times 10^8$  particles/kg or 660 TGPU per kg by IV infusion. See Table 2.

Pre-infusion, infusion (Day 1), and post-infusion follow up through Day 30 (+2 days) will be performed as outlined in *Table 4* below. Patients require observation at a minimum through the completion of Visit 4 (6 hours post-infusion). Patients may be admitted and observed overnight at the discretion of the PI. If the subject is an in-patient on Days 3-5, he/she should be assessed and samples collected as described in Table 4.

All patients in each cohort will be evaluated for any signs of AEs, serious adverse events (SAEs) and serious adverse drug reactions (SADRs) after infusion.

Patient infusions cannot occur on the same day. Once an enrolled patient has been infused, he/she must reach Day 4 without a suspension or stopping rule (1.9.8 Stopping Rules and Procedures for Study) event being reported prior to a subsequent patient being infused. In addition, there will be at least a two-week interval between cohorts to allow an independent Data Monitoring Committee (DMC) to review all patients' accumulated safety data after visit Day 6 from Cohort 1 and then again after the last patient from Cohort 2 has completed visit Day 6 in order to recommend whether the study should advance to the next cohort. Refer to Appendix B- Flow Diagram of Study Events.

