**Table 3 – List of Nominal Visits and Time-Points**

Nominal Visit/Time-Point	Scheduled Study Day	Day/Time Window
Screening 	Days -28 to Day -1	Any time during Days -28 to Day -1
Baseline	Day 1	Any time pre-infusion during Day 1 
Thrombosomes Infusion	Day 1	None; represents time-point 0 and provides reference for nominal visits and time-points
1-hour post-infusion	Day 1	±15 minutes
6-hour post-infusion	Day 1	-1 to +2 hours
24-hour post-infusion	Day 2	±3 hours
Day 3 	Day 3	Any time during Day 3
Day 4 	Day 4	Any time during Day 4
Day 5 	Day 5	Any time during Day 5
Day 6	Day 6	+4 days (any time during Days 6-10)
Day 30	Day 30	+2 days (any time during Days 30-32)

 If the patient is not actively bleeding at the time of screening but bleeding occurs within 4 days (+6 hours) of initial screening, the patient will not be rescreened (just WHO bleeding severity and CBC assessments will be repeated). If the patient is not actively bleeding at the time of screening but bleeding occurs >4 days and within 4 weeks of initial screening, the patient will be wholly rescreened and, following verification of eligibility, then enrolled and infused.

 Baseline assessments may occur any time preceding infusion on Day 1, except for the assessments of WHO bleeding severity, CBC, and coagulation. These assessments will be required to occur within the 2 hours preceding infusion.

 Relevant only if the patient is hospitalized.

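### SAP 9.2 counts transfused units since the previous assessment, so by-visit Day 6 transfusion results cover about 1 day for an inpatient and about 4 days or more for an outpatient

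*SAP*

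**What the plan says.** SAP 9.2 sets one counting rule for transfusions. "Within multiple tabular and graphic summaries of transfusions", the number of units at an assessment is the "total number of units transfused after the previous assessment and before/during the given assessment". Units "will be recorded from the onset of screening through Day 6".

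Two bar charts (Figures 14.2.2.4 and 14.2.2.5 in SAP Appendix 2) show the "mean number of platelet transfusions received per patient within the first 24 hours following infusion and during Days 3-6". The bars are dose cohorts, with "the clusters of bars (cohorts) being defined by nominal visit within the time-frame of interest". Tables 14.2.2.1 and 14.2.2.2 are also laid out by visit.

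The visits themselves are set elsewhere:

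- **Days 3-5.** SAP Table 3 footnotes the Day 3 visit with "Relevant only if the patient is hospitalized". Protocol 1.9.2.1 agrees: "If the subject is an in-patient on Days 3-5, he/she should be assessed and samples collected as described in Table 4".
- **Day 6.** SAP Table 3 gives this visit a window of plus "4 days (any time during Days 6-10" (closing bracket omitted).
- **24 hours.** This visit falls on Day 2, plus or minus 3 hours.
- **Care setting.** Protocol 1.9.2 describes the patients as hospitalized, but inclusion criterion 5 admits patients who are not, provided they can be observed in a clinic to 6 hours.

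SAP 2.2.2 makes post-infusion transfusion a secondary endpoint in two forms, the proportion of patients transfused and the number of units, each by cohort.

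**The concern.** A count over a period can be compared between groups only if the period is the same or is allowed for. Here its length is set by when the patient was last assessed, and that depends on care setting. For an outpatient, the last scheduled assessment before Day 6 is the 24-hour visit, so everything given after it is booked to Day 6. For an inpatient, the same units are spread over Days 3, 4, 5 and 6. Both kinds of patient sit in one cluster of a chart that exists to compare dose cohorts by eye.

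The cohorts are sequential, not randomized, and have 8 patients each. Nothing balances inpatient share or visit timing across them, and SAP 6.5 plans no stratified or adjusted analysis. A few more outpatients in one cohort could therefore look like a dose effect on transfusion use at Day 6. The SAP also does not say whether outpatients enter the Days 3-5 denominators as zeros or are left out.

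**Working it through.** The plan gives no figure to reproduce. The check is interval arithmetic on the visit schedule, followed by an illustration.

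**Step 1: length of the Day 6 interval.** Inputs: 24-hour visit on Day 2 (21 to 27 hours), Day 5 assessment for inpatients only, Day 6 visit on day d from 6 to 10 (all SAP Table 3). Visits are taken at the same clock time.

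- Outpatient: d − 2 days. For d = 6 this is 4 days (3.9 to 4.1 with the 3-hour window). For d = 10 it is 8 days (7.9 to 8.1).
- Inpatient assessed on Day 5: d − 5 days. For d = 6 this is 1 day; for d = 10 it is 5 days.

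With both patients seen on Day 6, the outpatient's value covers 4 times the inpatient's period.

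**Step 2: effect on cohort means.** Assume a constant rate r of platelet transfusions per day, equal in both cohorts. The documents give no rate, but r cancels from every ratio. Let p be the outpatient share and d the outpatients' Day 6 visit day. Inpatients are assessed daily and seen on Day 6, and units are counted up to the visit.

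- Day 6 bar = r × [p(d − 2) + (1 − p) × 1]
- Sum over Days 3-6 = r × [p(d − 2) + (1 − p) × 4]

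The reference cohort has p = 0, giving a bar of r and a sum of 4r.

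| Comparison cohort | Day 6 bar | Ratio | Sum | Ratio |
|---|---|---|---|---|
| 1 of 8 outpatients, d = 6 | (4 + 7)/8 = 1.375r | 1.375 | (4 + 28)/8 = 4r | 1.0 |
| Half outpatients, d = 6 | 0.5×4 + 0.5×1 = 2.5r | 2.5 | 0.5×4 + 0.5×4 = 4r | 1.0 |
| 1 of 8 outpatients, d = 10 | (8 + 7)/8 = 1.875r | 1.875 | (8 + 28)/8 = 4.5r | 1.125 |
| Half outpatients, d = 10 | 0.5×8 + 0.5×1 = 4.5r | 4.5 | 0.5×8 + 0.5×4 = 6r | 1.5 |
| All outpatients, d = 10 | 8r | 8.0 | 8r | 2.0 |

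Visit timing alone can also do this. If both cohorts are half outpatients, seen on Day 6 in one and Day 10 in the other, the bar ratio is 4.5/2.5 = 1.8 and the summed ratio is 6/4 = 1.5.

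**Step 3: what each cause does.** Care setting alone moves units between bars and leaves the sum unchanged. The sum moves only if Day 6 visits are late and units are counted up to the visit. In either setting, the first interval after the 24-hour visit also takes in units given later on Day 2, although the chart is labelled Days 3-6.

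**Step 4: Days 3-5 bars.** With half the cohort outpatients, each of these bars is 0.5r if outpatients count as zero and r if they are excluded. The SAP does not choose.

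**Step 5: under date-based assignment.** Every patient followed through Day 6 contributes calendar Days 3 to 6, which is 4 days, so the sum is 4r and the cohort ratio is 1.0 at equal true rates.

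**The case against.** The strongest objection concerns Days 7-10. A reader might infer from the visit window that units from those days certainly enter the Days 3-6 totals. The documents do not settle this. SAP 9.2 stops recording at Day 6, whereas SAP 8.1 speaks of the Day-6 visit and notes the possible extension to Day 10 when it means the windowed visit. The protocol's rule on blood counts around transfusions (Table 4, footnote 6) also refers to Days 1-6. A calendar cut-off is therefore a live reading. On the other side, transfusions are recorded in the Day 6 (+4 days) column of both schedules, and SAP Table 3 uses Day 6 as a visit name. The ambiguity stands, so the 8-day interval and the distorted total are conditional. The 4-to-1 mismatch at Day 6 is not.

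A reader might also infer that care setting biases the Days 3-6 total. It does not (Step 3). Nor should the gap between one outpatient's Day 6 value and one inpatient's be read as a cohort difference; that depends on the mix in each cohort.

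Other points stand in part:

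- Protocol 1.9.2 describes hospitalized patients, so outpatients may be few. With 1 of 8, the Day 6 bar ratio is 1.375 if seen on Day 6.
- The comparison is descriptive, with no test in SAP 9.2, and the endpoints in SAP 2.2.2 are not defined by visit. But the listed tables are by visit, the charts are by visit or over time, and no fixed-period total is listed.
- A patient-level listing is planned. It allows the figure to be corrected but does not correct it.
- The first-24-hour chart is unaffected, because all patients share those visits.

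**Conclusion.** The point holds for the by-visit results. Under the stated rule, the Day 6 transfusion tables and the Day 6 cluster of the Days 3-6 chart mix about 1 day of exposure (inpatient assessed on Day 5, seen on Day 6) with about 4 days (outpatient seen on Day 6). Against an all-inpatient cohort at equal true rates, a cohort that is half outpatients shows a Day 6 bar 2.5 times as high, with the summed total unchanged.

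If Day 6 means the visit, the outpatient interval can reach about 8 days. The same comparison with Day 10 visits then gives 4.5 for the bar and 1.5 for the sum. If it means the calendar day, essentially only the split by visit is affected, apart from the Day 2 units given after the 24-hour visit.

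These figures assume a constant and equal rate, daily inpatient assessment, and that an assessment means a nominal visit in SAP Table 3. Actual size and direction depend on outpatient share and visit dates in each cohort, which the documents do not give; cohorts alike in both would show no artificial difference. The effect is on a secondary-endpoint display, not on the primary safety analysis. The change should be made, but it is not critical.

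**What to change.** In SAP 9.2, replace the since-last-assessment rule for post-infusion summaries with assignment by each transfusion's actual date and time to fixed, contiguous intervals:

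- 0-24 hours after infusion
- 24 hours to the end of Day 2
- calendar Days 3, 4, 5 and 6, one interval each

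Cut at the end of calendar Day 6 for every patient. Use as denominator all patients still under observation in the interval, inpatient or outpatient, and state this. The second interval is needed so that units given after 24 hours on Day 2 are not lost. Say explicitly that Day 6 here is the calendar day.

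The cost is programming. Transfusion timing is already needed for the 24-hour baseline rule in SAP 9.2 and for Subgroups 3-6 in SAP 6.6, which are defined in hours from infusion. There are two downsides: units given on Days 7-10 would appear only in the listing, and outpatients' transfusion dates must be captured at the Day 6 visit.

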## **1.10 Study Population**

### **1.10.1 Patient Numbers**

Approximate number of patients screened: 120

Approximate number of patients consented: 60

Approximate number of patients enrolled: 30

Maximum Number of Patients Completed: 24 (8 patients in Cohorts 1-3)

Evaluable patients: 24

A patient is evaluable if they have completed their Day 6 follow up for Cohorts 1- 3.

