#### 2.1.2 Secondary Objective

The secondary objective of this study is to assess potential efficacy of Thrombosomes for managing bleeding in actively-bleeding, thrombocytopenic patients.

Efficacy will be assessed within and across 3 sequentially enrolled patient cohorts, treated, respectively, at 3 escalating dose levels (see *Primary Objective* above). Post-infusion patterns showing stability or change toward clinical improvement in hematology measures will be used as preliminary indicators of possible product efficacy in bleeding management, and patterns in the receipt of transfused blood products will also be examined.

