### 2.2.2 Secondary Endpoints

Multiple secondary endpoints will be quantified per patient cohort (i.e., by dose level), as well as overall (i.e., across all 3 dose levels):

- Number and percentage of patients who, from baseline to post-baseline time-points, show either stability (i.e., no change) or an intermittent or sustained change toward clinical improvement in hematology measures, with or without reaching normal levels.
- Number and percentage of patients who receive transfused blood products following infusion.
- Statistics describing central tendency and variability in the numbers of units of blood products transfused following infusion.

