### **5.2 Safety Population**

The Safety Population will include all patients who were infused with Thrombosomes, regardless of duration of subsequent study participation or adherence to planned follow-up assessments. As patients will be considered enrolled at the start of infusion, the Safety Population will also represent an "enrolled population". The population will be used in descriptive analysis of patient characteristics and disposition, as well as in all safety analyses supporting the Primary Objective and select efficacy analyses supporting the Secondary Objective.

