#### **6.4 Missing Values**

For all patients enrolled and all activities and assessments performed, every effort will be made to achieve complete data collection. Imputation is not planned for missing data, other than for missing date/time values. The missing component(s) of incomplete dates (e.g. start or stop dates of TEAEs, concomitant medication use, events/conditions in medical history) will be assumed to be the most conservative value possible. For example, if the start date is missing the day value, then the first day of the month will be imputed for study day computations. If the end date is missing the day value, then the last day of the month will be imputed. A similar approach will be used for missing month and year components. For complete dates but missing start or end times, values marking the beginning of the day (00:00:00AM) or end of the day (23:59:59PM), respectively, will be imputed. Importantly, date/time imputation will be used for computational purposes only; actual data values (as they appear in the database) will be presented in all patient-level data listings. Patients who withdraw consent for study participation or are lost to follow-up will be included in data summaries and analyses to the point of last contact.

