# 9 EFFICACY ANALYSES

All efficacy analyses will be performed using data collected from the Safety Population. For select hematology measures, however, analyses will be additionally performed using data from the Evaluable Population. Results will be presented in tables and figures and derived for individual patient cohorts (dose levels), as well as all patients combined (see **Appendix 2** for proposed data summaries). Data describing individual patients will be disclosed in data listings.

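### The transfusion summaries take no account of time alive and observed, so a patient who dies before any transfusion counts on the favourable side

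*SAP*

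**What the plan says.** SAP 2.1.2 makes potential efficacy the secondary objective and says that "patterns in the receipt of transfused blood products will also be examined". Two of the three secondary endpoints in SAP 2.2.2 concern transfusion: "Number and percentage of patients who receive transfused blood products following infusion" and "Statistics describing central tendency and variability in the numbers of units of blood products transfused following infusion". SAP 9.2 turns these into a table of patients transfused by visit, reason and product, a table of units by product and visit, spaghetti plots of platelet units, and bar charts by cohort of "the mean number of platelet transfusions received per patient within the first 24 hours following infusion and during Days 3-6".

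On who is counted, SAP 9 states that "All efficacy analyses will be performed using data collected from the Safety Population", and SAP 5.2 includes infused patients "regardless of duration of subsequent study participation or adherence to planned follow-up assessments". The repeat in the Evaluable Population is limited to selected hematology measures. SAP 6.4 says that patients who withdraw or are lost "will be included in data summaries and analyses to the point of last contact". It does not mention deaths and sets no denominator. SAP 6.6 defines subgroups by survival to Day 30, but the only stated use of them is for white cell counts (SAP 8.3).

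On timing, SAP 9.2 assigns to each assessment all units given since the previous one. Under SAP Table 3 the Day 3 to Day 5 visits apply only to hospitalized patients, and the Day 6 visit may fall anywhere from Day 6 to Day 10.

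**The concern.** A transfusion can be recorded only while a patient is alive and followed. A patient who dies on Day 2 cannot contribute to Days 3-6. One who dies before any transfusion enters the percentage endpoint as not transfused, alongside patients who survived without needing blood. The two outcomes are opposite but receive the same score.

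For mean counts, the plan leaves two readings open. Dividing by all infused patients adds zeros for those who have gone. Dividing by those still followed gives a mean among survivors. Two programmers could follow the SAP and report different figures. With 8 patients per cohort, one or two early exits are enough to change the comparison between dose levels that the cohort charts invite.

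**Working it through.** **The plan's own figures.** The documents give no transfusion rate, effect size or power for these endpoints, so there is nothing to reproduce beyond 3 × 8 = 24 patients, which is consistent.

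**Inputs.** Cohort size n = 8 (SAP 3.1). Days 3-6 = 4 days (SAP 9.2). Assumptions, not in the documents: a constant platelet transfusion rate λ = 0.5 per patient-day while followed (range 0.25 to 1.0), the same in every cohort, and k = 0 to 3 patients of 8 dead or withdrawn before Day 3.

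**Formulas for Days 3-6.**
- Mean over all infused = (8 − k) × λ × 4 / 8
- Mean over those still followed = (8 − k) × λ × 4 / (8 − k) = 4λ
- Rate per patient-day = (8 − k) × λ × 4 / [(8 − k) × 4] = λ
- Percentage transfused in the window, over all infused = [(8 − k)/8] × [1 − exp(−4λ)]

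**Results at λ = 0.5.**

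| Lost before Day 3 | Mean, all 8 | Change | Mean, still followed | Per 100 patient-days | % transfused, all 8 |
|---|---|---|---|---|---|
| 0 | 2.00 | 0 | 2.00 | 50 | 86% |
| 1 | 1.75 | −12.5% | 2.00 | 50 | 76% |
| 2 | 1.50 | −25.0% | 2.00 | 50 | 65% |
| 3 | 1.25 | −37.5% | 2.00 | 50 | 54% |

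The relative fall in the all-infused mean is k/8 whatever the rate. With 2 lost, the percentage transfused falls from 63% to 47% at λ = 0.25 and from 98% to 74% at λ = 1.0. True need is the same in every row.

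**Is the direction for means fixed?** Let 2 of 8 die at the end of Day 3 after using platelets at m times the usual rate on that day. The all-infused mean is (6 × 0.5 × 4 + 2 × 0.5 × m)/8 = (12 + m)/8. This gives 1.625, 1.75, 2.00 and 2.25 for m = 1, 2, 4 and 6, against 2.00 with no deaths. The rate over 6 × 4 + 2 × 1 = 26 patient-days is 50.0, 53.8, 61.5 and 69.2 per 100. So the crude mean can fall, stay level or rise, while the rate shows the heavier use.

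A second check takes a whole period in which 2 of 8 leave halfway with relative need r, compared with a cohort of ordinary need and no losses. The ratio of means is 0.75 + 0.25 × r × 0.5, which is 0.875, 1.00 and 1.125 for r = 1, 2 and 3.

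**Unequal time among survivors.** Take a patient with no visit between 24 hours (Day 2) and the Day 6 visit. If recording runs to that visit, the expected count is 0.5 × 4 = 2.0 when seen on Day 6 and 0.5 × 8 = 4.0 when seen on Day 10.

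**The case against.** The strongest reply is that the planned layout already limits the problem. Units are tabulated by visit, the bars are clustered by nominal visit, and SAP 6.9 includes the number of patients in continuous summaries. SAP 6.4 carries withdrawn and lost patients only to last contact. The natural reading is then a mean over patients still followed, which shows no false reduction at equal need. This stands as a likely reading. However, the SAP does not state it, it gives no rule for deaths, and it leaves a survivors-only mean. It also does not help the SAP 2.2.2 percentage, if that is read as cumulative over all infused patients.

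Early exits are also visible elsewhere: disposition by cohort, the treatment-emergent deaths table, the deaths listing, the transfusion listing and the individual plots. A careful reader of 8 patients could piece the picture together. That is true, but no planned summary does so. Exits also matter little for the 24-hour chart unless they occur within 24 hours.

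Two stronger readings are tempting.

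- A reader might infer that the bias always favours the product, so that toxicity would appear as transfusion sparing. The documents do not support this for mean counts: the checks above give no difference or more units once departing patients use enough before they leave.
- A reader might set the Protocol 1.10.1 line "Approximate number of patients enrolled: 30" against 24 evaluable patients and infer that 20% of infused patients will be lost. The protocol does not define enrolled, as SAP 11 itself notes, and SAP 3.1 plans 24 enrolled in three cohorts of 8. Missing evaluability means only a missed Day 6 visit, not death, and Protocol Table 6 asks sites to continue visits or calls after withdrawal. The 20% figure should not be used.

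**Conclusion.** The omission is real, and neither document repairs it. For the percentage transfused following infusion, taken over all infused patients, the direction is certain: death before any transfusion scores as favourable. For mean counts on Days 3-6, the size is 12.5% per patient of 8 lost before Day 3. That figure assumes that departed patients stay in as zeros and that need is equal and constant. With a denominator of those still followed, the false reduction disappears at equal need, but the mean then describes survivors only. Neither the number of early exits nor the transfusion rate is given in the documents, so the overall effect cannot be predicted.

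The consequence is limited. No transfusion test is planned, the sample size has no statistical basis, and the primary objective is safety. What is at risk is a descriptive comparison between dose cohorts. This is a worthwhile, inexpensive improvement and not a threat to the trial's main conclusions.

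**What to change.** In SAP 9.2, keep the planned tables and figures and state the denominator at each visit as patients alive and followed. Then add, by cohort:

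- **Rate.** Units per patient-day alive and observed, by product type, from infusion to the earliest of death, last contact or the end of Day 6. The fixed end also removes the unequal time created by the Day 6 visit window.
- **Outcome that accounts for death.** Number and percentage alive and transfusion-free through 24 hours and through Day 6. Death before the time-point counts as not meeting the outcome, and withdrawals are shown in a separate row.

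The cost is SAP wording, two derived variables from transfusion, death and last-contact records, and a few extra rows in Tables 14.2.2.1 and 14.2.2.2. No extra patients or visits are needed. Both additions have limits. With 8 patients, one short and heavily transfused follow-up can dominate the rate. The composite is not specific to bleeding, because SAP 9.2 lists low platelet count, chronic disease and marrow hypoplasia among the reasons for transfusion. Both should therefore be labelled descriptive supplements.
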